14.4.3. Recording Adverse Events

Throughout the study, the investigator will record adverse events and serious adverse events as described previously (Section 14.2, *Definitions*) on the appropriate AE/SAE eCRF regardless of the relationship to study therapy regimen or study procedure.

Once recorded, an AE/SAE will be followed until it resolves with or without sequelae, or until the end of study participation, or until 30 days after the subject prematurely withdraws (without withdrawing consent)/or is withdrawn from the study, whichever occurs first.

14.5. Reporting of Serious Adverse Events and Adverse Events**14.5.1. Reporting of Serious Adverse Events to Sponsor**

This section describes the responsibilities of the site investigator to report serious adverse events to the sponsor via the AE/SAE eCRF. Timely reporting of adverse events is required by 21 CFR and ICH E6 guidelines.

Site investigators will report all serious adverse events (see Section 14.2.3, *Serious Adverse Event*), regardless of relationship or expectedness within 24 hours of discovering the event.

For serious adverse events, all requested information on the AE/SAE eCRF will be provided. However, unavailable details of the event will not delay submission of the known information. As additional details become available, the AE/SAE eCRF will be updated and submitted.

14.5.2. Reporting to Health Authority

After an adverse event requiring 24-hour reporting (per Section 14.5.1, *Reporting of Serious Adverse Events to Sponsor*) is submitted by the site investigator and assessed by DAIT/NIAID, there are two options to report the adverse event to the appropriate health authorities:

14.5.2.1 Annual Reporting

DAIT/NIAID will include in the annual study report to health authorities all adverse events classified as:

- Serious, expected, suspected adverse reactions (see Section 14.2.1.1, *Suspected Adverse Reaction*, and Section 14.2.2, *Unexpected Adverse Event*).
- Serious and not a suspected adverse reaction (see Section 14.2.1.1, *Suspected Adverse Reaction*).
- Pregnancies.

Note that all adverse events (not just those requiring 24-hour reporting) will be reported in the Annual IND Report.

14.5.2.2 Expedited Safety Reporting

DAIT/NIAID shall notify the FDA and all participating investigators of expedited Safety Reports within 15 calendar days; unexpected fatal or immediately life-threatening suspected adverse reaction(s) shall be reported as soon as possible or within 7 calendar days.

This option, with 2 possible categories, applies if the adverse event is classified as one of the following:

Category 1: Serious and unexpected suspected adverse reaction [SUSAR] (see Section 14.2.1.1, *Suspected Adverse Reaction* and Section 14.2.2, *Unexpected Adverse Event* and 21 CFR 312.32(c)(1)i).

The sponsor shall report any suspected adverse reaction that is both serious and unexpected. The sponsor shall report an adverse event as a suspected adverse reaction only if there is evidence to suggest a causal relationship between the study drug and the adverse event, such as:

1. A single occurrence of an event that is uncommon and known to be strongly associated with drug exposure (e.g., angioedema, hepatic injury, or Stevens-Johnson Syndrome);
2. One or more occurrences of an event that is not commonly associated with drug exposure, but is otherwise uncommon in the population exposed to the drug (e.g., tendon rupture);
3. An aggregate analysis of specific events observed in a clinical trial (such as known consequences of the underlying disease or condition under investigation or other events that commonly occur in the study population independent of drug therapy) that indicates those events occur more frequently in the drug treatment group than in a concurrent or historical control group.

Category 2: Any findings from studies that suggests a significant human risk

The sponsor shall report any findings from other epidemiological studies, analyses of adverse events within the current study or pooled analysis across clinical studies or animal or *in vitro* testing (e.g., mutagenicity, teratogenicity, carcinogenicity) that suggest a significant risk in humans exposed to the drug that would result in a safety-related change in the protocol, informed consent, investigator brochure or package insert or other aspects of the overall conduct of the study.

14.5.3. Reporting of Adverse Events to IRBs/IECs

All investigators shall report adverse events, including expedited reports, in a timely fashion to their respective IRBs/IECs in accordance with applicable regulations and guidelines. All Safety Reports to the FDA shall be distributed by DAIT/NIAID or designee to all participating institutions for site IRB/IEC submission.

14.6. Pregnancy Reporting

The investigator shall be informed immediately of any pregnancy in a study subject or a partner of a study subject. A pregnant subject shall not receive Tregs, and will be instructed to stop taking everolimus, if applicable. The investigator shall counsel the subject and discuss the risks of continuing with the pregnancy and the possible effects on the fetus. Monitoring of the pregnant subject shall continue until the conclusion of the pregnancy.

The investigator shall report to the Statistical and Clinical Coordinating Center (SACCC) all pregnancies within 1 business day of becoming aware of the event using the Pregnancy eCRF. All pregnancies identified during the study shall be followed to conclusion and the outcome of each must be reported. The Pregnancy eCRF shall be updated and submitted to the DAIT/NIAID via the SACCC when details about the outcome are available. When possible, similar information shall be obtained for a pregnancy occurring in a partner of a study subject.

Information requested about the delivery shall include:

1. Gestational age at delivery
2. Birth weight, length, and head circumference
3. Gender
4. Appearance, pulse, grimace, activity, and respiration (APGAR) score at 1 minute, 5 minutes, and 24 hours after birth, if available
5. Any abnormalities.

All pregnancy complications that result in a congenital abnormality, birth defect, miscarriage, and medically indicated abortion - an SAE shall be submitted to the DAIT/NIAID via the SACCC using the SAE reporting procedures described above. Pregnancies reported as SAE's will be reported to the FDA as described above.

14.7. Reporting of Other Safety Information

An investigator shall promptly notify the site IRB as well as the SACCC using the AE/SAE eCRF when an "unanticipated problem involving risks to subjects or others" is identified, which is not otherwise reportable as an adverse event.

14.8. Review of Safety Information

14.8.1. Medical Monitor Review

The PI, Protocol Chair, and NIAID Medical Monitor will review safety data on an ongoing basis. Enrollment and initiation of study treatment may be suspended at any time if these reviews conclude that there are significant safety concerns.

In addition, the Medical Monitor shall review and make decisions on the disposition of the SAE and pregnancy reports received by the SACCC in a timely manner.

14.8.2. Planned DSMB Reviews

The Data and Safety Monitoring Board (DSMB) shall review safety data at least yearly during planned DSMB Data Review Meetings. Data for the planned safety reviews will include, at a minimum, a listing of all reported AEs and SAEs.

The DSMB will be informed of an Expedited Safety Report in a timely manner.

14.8.3. *Ad hoc* DSMB Reviews

In addition to the pre-scheduled data reviews and planned safety monitoring, the DSMB may be called upon for *ad hoc* reviews. The DSMB will review any event that potentially impacts safety at the request of the PI, protocol chair or DAIT/NIAID. After review of the data, the DSMB will make recommendations regarding study conduct and/or continuation.

15. Statistical Considerations and Analytical Plan

15.1. Overview

CTOT-21 is a Phase 2 open label study, in which 14 adult kidney transplant recipients will be allocated to one of 2 treatment arms: CNI-only, or polyTregs. Subjects allocated to the Treg treatment arm will receive a single infusion of polyTregs approximately 7 months after transplant. The primary safety objective is to evaluate the safety of polyTregs in adult kidney transplant recipients. The primary efficacy objective of the study is to evaluate whether polyTregs reduce graft inflammation when compared to CNI-based maintenance therapy.

15.2. Measures to Minimize Bias

The study groups will be assigned in an un-blinded fashion using a variation of the Pocock and Simon adaptive randomization algorithm designed to maintain an overall 1:1 ratio. Centralized laboratories will be used to minimize bias and mechanistic core laboratory personnel, including the core pathologist, will be blinded to study treatment assignments. Clinical sites will not be blinded to treatment assignments and reports for site use and monitoring purposes will not be blinded.

15.3. Analysis Plan

Statistical analyses of the safety and clinical outcomes will be performed for the analysis samples defined below in section 15.3.1, employing standard methods for the estimation of incidence rates and their exact two-sided 95% confidence intervals. Statistical analyses of most mechanistic outcomes will be exploratory in nature. The subject enrolled and treated in the darTreg arm, prior to the removal of that treatment arm in protocol version 9.0, will be individually summarized, including but not limited to adverse events, infusion details, and inflammation scores and changes. The plans for statistical analyses of study data will be described in more detail in a Statistical Analysis Plan (SAP).

15.3.1. Analysis Samples

The statistical analyses will be performed on the following subject samples:

1. The Modified Intent-to-Treat Sample 1 (mITT1) consists of all subjects allocated to the CNI-based treatment regimen or received polyTregs while on study.
2. The Per Protocol Sample (PP) consists of all subjects allocated to the CNI-based treatment regimen or received at least 300×10^6 of polyTregs while on study that did not have major protocol deviations of concern.
3. The modified intent-to-Treat Sample 2 (mITT2) consists of all subjects who received polyTregs (Group 2).

15.3.2. Endpoint Assessments

15.3.2.1 Primary and Secondary Safety Endpoints

Table 7. Analyses of Safety Endpoints describes the safety endpoints and their corresponding parameters to be estimated in the study. Safety endpoints will be listed or summarized, as appropriate, using standard descriptive statistics for continuous and categorical data.

Table 7. Analyses of Safety Endpoints

ENDPOINT	DESCRIPTIVE PARAMETER	ANALYSIS POPULATION
Primary Endpoint		
Incidence of severe acute rejection or antibody mediated rejection in subjects receiving polyTregs in comparison with CNI-based maintenance IS therapy.	Proportion with exact binomial 95% confidence limits	miITT1
Incidence of severe infection in subjects receiving polyTregs in comparison with CNI-based maintenance IS therapy.	Proportion with exact binomial 95% confidence limits	miITT1
Secondary Endpoints – Treg safety		
Incidence of polyTregs infusion reactions (episodes of fever, bronchospasm, hypoxia, cytokine release syndrome, or infusion site reaction)	Proportion with exact binomial 95% confidence limits	miITT2
Severity of polyTregs infusion reactions	Descriptive CTCAE categories	miITT2
Incidence of culture-proven and clinically diagnosed infections	Proportion with exact binomial 95% confidence limits	miITT1
Severity of culture-proven and clinically diagnosed infections	Descriptive CTCAE categories	miITT2
Incidence of severe infection in subjects receiving polyTregs in comparison with CNI-based maintenance IS therapy.	Proportion with exact binomial 95% confidence limits	miITT1
Timing of acute rejection	Mean time to rejection and standard deviation	miITT1
Incidence of acute rejection	Proportion with exact binomial 95% confidence limits	miITT1
Severity of acute rejection	Descriptive Banff criteria	miITT1
Incidence of CMV reactivation	Proportion with exact binomial 95% confidence limits	miITT1
Incidence of BK viremia	Proportion with exact binomial 95% confidence limits	miITT1
Incidence of >10% decrease in eGFR from baseline	Proportion with exact binomial 95% confidence limits	miITT1
Secondary Endpoints – mTOR therapy		
Incidence of acute rejection	Proportion with exact binomial 95% confidence limits	miITT2 (Treg mTOR vs Treg no mTOR)

15.3.2.2 *Supportive Analyses of the Primary Safety Endpoints*

Although the study is not powered to detect clinically significant differences in safety event incidence between treatment groups, in a supportive analysis, the incidence of the composite endpoint will be compared between the two treatment groups by an overall Fisher's exact test using the miITT1 analysis sample to compare the incidence between the two groups.

15.3.2.3 Primary Efficacy Endpoint

The primary efficacy endpoint is the mean change from baseline in percent inflammation on biopsy at 7 months and it will be compared between the two treatment groups by ANOVA using the mITT1 analysis sample. The primary endpoint data will be summarized in the 2 groups using boxplots, along with means and 95% confidence intervals.

15.3.2.4 Secondary Efficacy Endpoints

Table 8 describes secondary efficacy endpoints and their corresponding parameters to be estimated in the study.

Efficacy endpoints will be listed or summarized, as appropriate, using standard descriptive statistics for continuous and categorical data, including confidence intervals. All secondary endpoints will be descriptive in nature due to the small sample size.

Table 8. Analyses of Secondary Efficacy Endpoints		
SECONDARY ENDPOINT	DESCRIPTIVE PARAMETER	ANALYSIS SAMPLE*
Number of subjects who exhibit a relative decrease of 25% or more inflammation on kidney biopsy 7 months after study group allocation compared to baseline	Proportion with exact binomial 95% confidence limits	mITT1
Number of subjects who exhibit a relative decrease of 25% or more inflammation on kidney biopsy 2 weeks after Treg infusion compared to baseline	Proportion with exact binomial 95% confidence limits	mITT2
Number of subjects who exhibit a relative decrease of 50% or more inflammation on kidney biopsy 2 weeks after Treg infusion compared to baseline	Proportion with exact binomial 95% confidence limits	mITT2

15.3.2.5 Supportive Analyses of the Primary Efficacy Endpoints

In addition to the primary efficacy endpoint analysis described above, several supportive analyses will be performed:

1. Since the occurrence of treated rejection prior to or at the time of the 7 month biopsy may confound the measurement of inflammation, the ANOVA described above will be repeated deleting any subjects from the analysis who had treated rejection prior to the 7 month biopsy.
2. Since clinical site, donor type, and race may confound the interpretation of the primary analysis, ANCOVA will be used to separately test for the effect of site, donor type, and race on the primary endpoint analysis.
3. If the PP sample differs from the mITT1 sample, the primary endpoint analysis will be repeated on the PP analysis sample.

15.3.2.6 Mechanistic Endpoints

Three of the mechanistic assays, CRM, SORT, and DEU, which have high level of sensitivity and specificity, will be used to evaluate mechanistic efficacy endpoints (Table 9).

Table 9. Analysis of mechanistic endpoints

Endpoints	Assays	Measurements
Pharmacokinetics of infused Tregs in blood and graft	DEU[¶]	% deuterium enrichment in blood and graft
Rejection gene in blood	SORT[¶]	Pearson's Correlation Coefficient based Z score; $Z = \chi - \mu_{global} / \sigma_{global}$
Inflammatory gene in graft	CRM[¶]	Geometric mean score of the expression of 11 of the 12 CRM genes in each sample

[¶]DEU, SORT and CRM assays are for evaluation of efficacy endpoints

15.3.2.7 Analyses of Exploratory Endpoints

Planned mechanistic assays other than CRM, SORT, and DEU are for exploratory assessment of the impact of specific therapies on inflammation and borderline rejection. Any statistically significant results from these tests will be reported as requiring independent verification and will provide a basis for further studies.

Treatment groups and comparators: We will analyze the readouts on assays longitudinally. Patient measurements will be obtained before and after treatment. There will be at least 2 time points recorded for the TASK trial (before and after Treg infusion). The primary interest of analysis is to compare longitudinal changes in assays between different groups: SCI with SOC, and SCI with polyTregs. Two groups of patients, those with normal histology and those with acute rejection on the 6-month surveillance biopsy, will serve as negative and positive controls respectively for the mechanistic studies. We expect the changes over time in these assays to be approximately linear. If after examination of the data appears to not be the case then we will either transform the assay measures or model the time axis time points as an unordered factor (similar to repeated measures ANOVA, but without the requirement for fully balanced data).

Table 10. Analysis of exploratory mechanistic endpoints

Endpoints	Assays	Measurements
Total Tregs in blood and graft	MFC	% and absolute numbers of Tregs
	miHc	% FOXP3+ among CD3+ cells
Infused Tregs in blood and graft	TCR*	# and frequency of clones from Treg product
Cellular alloimmune profile	MFC	% and absolute numbers of various cell subsets
	SUPP	% suppression at 1 Treg:4 PBMC ratio
Cellular viral immune profile	VIR	Frequencies of CMV and EBV reactive CD8 T cells; % polyfunctional anti-viral T cells
Antibody responses	HLA	DSA+ or DSA-; MFI if DSA+
	nHLA	Concentration of antibodies to 6 nHLA antigens
Immune tolerance gene in blood	SPOT	Penalized Logistic Regression score for 3 genes
Inflammation in graft	HIS	% inflammatory cell load by area; % area with interstitial fibrosis
IL6 signaling in the graft	miF ISH [§]	+cells /high power field; number of ISH dots/high power field
Graft fibrosis	FIB	Concentration of protein associated with tubular injury; concentration of pro-fibrotic proteins
	uFIB	Concentration of protein associated with fibrosis
Inflammation markers in urine	uPRO	Concentration of proteins associated with kidney injury and inflammation in urine
	uRNA	Absolute copy number of mRNA for genes associated with acute rejection

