1.1. Hypotheses

This study will explore the following hypotheses:

1. PolyTreg infusions are safe and will increase the absolute number of Tregs in circulation and in the kidney allograft.
2. PolyTregs will suppress inflammation in the graft and reduce markers of inflammation in the graft and urine

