11.1.3. Peripheral Blood Treg Number (MFC-Treg)

Blood (1 ml) will be collected at visits specified in the schedule of events (Appendix 2 and 3), processed into PBMC, and cryopreserved for batched analysis. Percentage of Tregs among CD4 T cells will be determined using multiparameter flow cytometry (MFC) as described in section 11.3.1 below. The absolute number of peripheral blood Tregs will be calculated using the number of CD4 counts obtained from clinical lab test.

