11.1.4. Treg TruCount Analysis

Samples collected for this assay will be used directly for analysis without cryopreservation. Blood will be aliquoted into a TruCount tube, stained with fluorochrome-conjugated antibodies to CD4, CD45, CD25 and CD127, and analyzed on a flow cytometer to enumerate the numbers of Tregs.

This assay would allow us to obtain the absolute Treg counts in one microliter of blood.

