11.2. Impact of Treg Infusion on Graft Inflammation

11.2.1. Detection of Intragraft Inflammation by Multiplexed Immunofluorescence and *in situ* Hybridization (mIF/ISH)

Histopathology combined with immunohistochemistry (IHC) or immunofluorescence (IF) provides information on the location, nature, and magnitude of the inflammatory response, but traditionally is not a reliable approach for quantifying changes in inflammatory mediators. To quantitatively assess cytokine expression in the graft tissue in response to intervention, the [name] lab has adapted the RNAscope® *in situ* hybridization (ISH) platform to analyze formalin-fixed paraffin-embedded biopsies. Furthermore, a novel technology that combines ISH with IF was developed and optimized for various targets; this highly sensitive and specific ISH/IF methodology combined with computer-assisted image analysis allows precise quantitative phenotypical analysis of immune infiltrates and parenchymal cells along with their gene expression profiles in the biopsy tissue. We plan to use this technology to assess change in inflammatory and tolerance markers in the grafts after Treg therapy in biopsy samples obtained at 2 weeks and 6 months after Treg infusion and compared to the baseline in the eligibility biopsy samples. The following structural and inflammatory markers will be evaluated using IHC/IF technology: collagen 3 for interstitial fibrosis, and CD4, CD8, Treg (FoxP3), CD20, and CD68 for inflammation. ISH IL-6 mRNA will be detected via ISH. Any for-cause biopsies performed during the study will also be evaluated using the same parameters.

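### Hypothesis 1 concerns the absolute number of Tregs in the allograft, but the only planned tissue readout of total graft Tregs is a proportion, which can disagree with that number in size or direction

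*Protocol*

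**What the plan says.** Hypothesis 1 (Protocol section 1.1) is that polyTreg infusions are safe and "will increase the absolute number of Tregs in circulation and in the kidney allograft". The target is therefore an absolute number, in two compartments.

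Table 10 (section 15.3.2.7) has one row on total Tregs, covering blood and graft together, with two assays:

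- Multiparameter flow cytometry (MFC), reported as percentage "and absolute numbers of Tregs".
- A tissue stain labelled miHc, reported as the percentage "FOXP3+ among CD3+ cells".

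The assay sections show which compartment each absolute count belongs to. Section 11.1.3 on MFC says: "The absolute number of peripheral blood Tregs will be calculated using the number of CD4 counts obtained from clinical lab test". Section 11.1.4 on TruCount says: "This assay would allow us to obtain the absolute Treg counts in one microliter of blood". Appendices 2 and 3 list both assays under blood specimens, and TruCount is done only at screening.

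Section 11.2.1 gives the tissue markers as "collagen 3 for interstitial fibrosis, and CD4, CD8, Treg (FoxP3), CD20, and CD68 for inflammation". SAP section 8.3 adds no specific graft Treg measure; it leaves the remaining mechanistic data to general summary statistics.

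**The concern.** The blood half of Hypothesis 1 has a readout of the quantity it names. The graft half does not. It has a ratio whose denominator is made up of the cells that the treatment may reduce.

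Hypothesis 2 in the same section is that polyTregs suppress graft inflammation. If conventional T cells leave the graft while FOXP3+ cells stay, the percentage goes up with no Treg added. A report could then read a shrinking infiltrate as Treg accumulation. The reverse error is also possible: if the whole infiltrate grows in proportion, Treg numbers rise and the percentage does not move.

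At stake is the interpretation of one mechanistic hypothesis. No decision on efficacy or safety depends on it.

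**Working it through.** The plan gives no figure for this readout, so there is nothing to reproduce. The check has two parts.

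**1. Is there another readout of total graft Tregs?**

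| Readout | Where | Compartment | Quantity |
|---|---|---|---|
| MFC | 11.1.3, 11.3.1, Table 10 | blood | percentage and absolute, total Tregs |
| TruCount | 11.1.4 | blood, screening only | absolute, total Tregs |
| miHc | Table 10 | graft | percentage of CD3+ cells, total Tregs |
| Deuterium | 11.1.1, 11.1.2, Table 9 | blood; graft at 2 weeks, Group 2 | percent enrichment, infused cells |
| T cell receptor | 3.6.1, Table 10 | blood and graft, Group 2 | clones from the infused product |

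Only miHc addresses total Tregs in graft tissue, and it is a proportion.

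**2. How does the proportion behave?**

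Let F be FOXP3+ CD3+ cells and O other CD3+ cells per unit of tissue. The share is F / (F + O). It rises if and only if F is multiplied by a larger factor than O. The documents give no baseline share and no expected change in CD3+ cells, so both are assumptions. Starting points are F = 5, O = 95 (5%) and F = 10, O = 90 (10%).

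| Change | From 5% | From 10% | Absolute Tregs |
|---|---|---|---|
| O down 25%, F fixed | 5/(5+71.25) = 6.6% | 10/(10+67.5) = 12.9% | unchanged |
| O down 50%, F fixed | 5/(5+47.5) = 9.5% | 10/(10+45) = 18.2% | unchanged |
| O down 75%, F fixed | 5/(5+23.75) = 17.4% | 10/(10+22.5) = 30.8% | unchanged |
| O down 50%, F down 25% | 3.75/(3.75+47.5) = 7.3% | 7.5/(7.5+45) = 14.3% | down 25% |
| O and F both down 50% | 5.0% | 10.0% | down 50% |
| O down 50%, F down 60% | 2/(2+47.5) = 4.0% | 4/(4+45) = 8.2% | down 60% |
| O and F both doubled | 5.0% | 10.0% | doubled |

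From an assumed 20% baseline, a 50% fall in O with F fixed gives 20/(20+40) = 33.3%.

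With F fixed and O halved, the apparent rise is 1.90-fold from 5%, 1.82-fold from 10% and 1.67-fold from 20%. The fourth row shows a disagreement in direction: the percentage rises while the number of Tregs falls. The last row shows a doubling that the percentage misses.

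**The case against.** The strongest case against is that this is an exploratory readout in a pilot with 7 per arm. Section 1.1 says the hypotheses will be explored, and section 15.3.2.7 says that significant results from these assays need independent verification. SAP section 8.3 is general enough for a density to be reported without changing any specified analysis. This stands, and it limits the severity. It does not supply the missing quantity.

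Four stronger readings are tempting, and the documents do not support them.

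- **A reader might infer that the percentage rises whenever other T cells fall.** It does not: in the table it is flat when both populations halve, and it falls when FOXP3+ cells fall more. Section 2.3 links rejection and borderline change with more Tregs in the graft, so endogenous graft Tregs could decline as inflammation resolves. Hypothesis 2 also makes no statement about CD3+ cells. A falling denominator is plausible, not given.
- **A reader might infer that the trial cannot tell whether infused cells reached the graft.** The deuterium biopsy assay (section 11.1.2) is designed for that question, and Table 9 makes deuterium one of three assays used for mechanistic efficacy endpoints. The gap concerns total Tregs only.
- **A reader might infer that CD3 is not stained, so the percentage cannot be computed.** Section 11.2.1 does not name CD3, but its list also omits the pan-leukocyte marker (LCA/CD45) used for total inflammatory load in sections 2.1.2.2 and 11.2.2. Section 2.1.2.2 also leaves its marker list open-ended. CD3 is unspecified, not excluded.
- **A reader might take 1.9-fold as the largest artefact.** It reflects only the assumed 50% fall; a 75% fall from 5% gives about 3.5-fold.

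**Conclusion.** The mismatch is real and narrow. Hypothesis 1 names an absolute number in the allograft, and the only planned tissue readout of total graft Tregs is a share of CD3+ cells. That share cannot separate more Tregs from fewer other T cells, and it can move against the absolute number.

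The illustrated size is 5% to 6.6% or 9.5%, and 10% to 12.9% or 18.2%, for falls of 25% or 50% in other CD3+ cells with no change in Tregs. The baselines and the falls are assumptions, and the results are neither forecasts nor upper limits. That the share and the number can differ does not depend on them.

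The primary and secondary endpoints, the sample size and the safety rules do not use this readout. The severity is low.

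**What to change.** In Table 10, add FOXP3+ cells per mm2 of cortex as the graft readout for Hypothesis 1, and keep the percentage of CD3+ cells as a companion descriptor. If cortical area is not measured on the FoxP3 sections, FOXP3+ cells per high power field would serve. Make the change before the graft FoxP3 results are examined by group, so that nobody chooses between count and ratio afterwards.

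The cost is one extra image-analysis output and a line of wording. FoxP3 is already in the section 11.2.1 stain list, computer-assisted image analysis is already planned there, and per-area counts are already used elsewhere: infiltrating cells per square mm in the introduction to section 6, and positive cells per high power field for IL6 signalling in Table 10.

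As a minor editorial point, state which stained markers form the denominator of the percentage, either by naming CD3 in section 11.2.1 or by defining the denominator from listed markers such as CD4 and CD8. If CD3 turns out not to be stained, adding it would cost a further stain; using the listed markers would not.

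If no density is added, the alternative is to reword the graft part of Hypothesis 1 as a proportion.
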